#### 4.8 Termination criteria

- (1) Patient requests to withdraw from the study.

### 5 Observation Cohorts and Treatments

#### 5.1 Treatment Allocation by Cohort

- Chinese Medicine Group: Chinese treatments, which may include herbal formulas (e.g., decoctions, granules) or acupuncture, tailored to their syndrome differentiation (e.g., heat-clearing, detoxifying, or dampness-resolving therapies).;

- Western medicine group: Patients receive only standard Western medical care, which may include antipyretics (e.g., acetaminophen), NSAIDs for pain, and supportive treatments (e.g., hydration);
- Integrated therapy group : receive both Chinese and Western treatments.

## 5.2 Observation period and follow-up

Maximum observation period: 28 days

Visit time:

Screening period/baseline: First visit D0, with lab assessments: complete blood count, CRP, and chikungunya nucleic acid tests;

Treatment observation period: D1-D5, daily follow-up with clinical and lab assessments, D5 or before discharge: complete blood count, CRP, and chikungunya nucleic acid tests;

Follow-up after treatment; telephone follow-up on D7, D14, and D28.

On D0, D5 or before discharge, collect 8 ml of whole blood (anticoagulant tube) for storage.

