**Flow chart**

Stage	Screening Period / Baseline	Treatment observation period							Follow-up after treatment (telephone follow-up)		
		Visit 1 D0	Visit 2 D1	Visit 3 D2	Visit 4 D3	Visit 5 D4	Visit 6 D5	Visit X Before discharge	Visit 7 D7	Visit 8 D14	Visit 9 D28
Visit point (D, day)											
Informed consent form	×										
Chikungunya RNA test	×						×	×			
Epidemiological data	×										
General information and medical history	×										
Physical examination, vital signs	×				×		×	×			
Body temperature	×	Patient diary card for body temperature record									
Chikungunya Symptom Scale	×	×	×	×	×	×	×	×	×	×	×
Complication		×	×	×	×	×	×	×	×	×	×
Severe / critical illness		×	×	×	×	×	×	×	×	×	×
Laboratory tests	×						×	×			
Patient diary card collection	×						×	×			
Medication records	×	×	×	×	×	×	×	×			
Adverse Events		×	×	×	×	×	×	×	×	×	×

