#### 3.2 Visit

Screening period/baseline: First visit D0, complete blood count, CRP, chikungunya nucleic acid and liver and kidney function tests

Treatment observation period: D1-D5, daily follow-up, filling in the CRF, collecting the complete blood count, CRP, and Chikungunya fever nucleic acid results on D5/Discharge day.

Follow-up after treatment; telephone follow-up was conducted on D7, D14, and D28.

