#### ■ VAS (Visual Analog Scale) pruritus score

No itching at all 0--1--2--3--4--5--6--7--8--9 — 10 Worst itching point

**(3) Complete fever reduction time: Complete fever reduction is defined as the body temperature dropping to 37.2°C or below after the first dose and maintained for 24 hours or more;**

(4) Nucleic acid negative conversion time;

(5) Time for single symptom to disappear;

(6) Overall symptom disappearance time;

(7) Time for white blood cell count to return to normal: the time from the first dose to the first observation of white blood cell count returning to normal;

(8) Time for platelet count to return to normal: the time from the first dose to the first observation of platelet count returning to normal;

(9) Incidence of Chikungunya-related complications: Proportion of patients with recorded AEs for Chikungunya-related complications (shock, DIC, encephalitis, acute liver injury, acute kidney injury, myocarditis, pericarditis, pneumonia, respiratory failure, rhabdomyolysis, acute pancreatitis) after the start of treatment.

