### 6.3 Safety Information

(1) Laboratory tests such as complete blood count/liver and kidney function , chest CT/X-ray, electrocardiogram: collected based on actual clinical situations ;

(2) Incidence of adverse events/adverse reactions.

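### The D1–D5 laboratory schedule can be read as daily or as D5/discharge only, and recorded white-cell, platelet and RNA recovery times depend on which reading a centre follows

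*Protocol*

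**What the plan says.** Four places in the protocol describe laboratory testing between D1 and D5.

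- **Program summary and section 5.2.** Both have "Treatment observation period: D1-D5, daily follow-up with clinical and lab assessments". In both, the sentence then continues and names blood count, CRP and the RNA test at D5 or before discharge.
- **Section 3.2.** It has "daily follow-up, filling in the CRF, collecting the complete blood count, CRP, and Chikungunya fever nucleic acid results on D5/Discharge day". Nothing here attaches laboratory work to D1–D4.
- **Flow chart.** The rows "Chikungunya RNA test" and "Laboratory tests" each carry three marks: baseline, D5 and before discharge. There is none on D1–D4.

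Section 6.3 adds that safety laboratory tests are "collected based on actual clinical situations", so it sets no common frequency either.

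The outcomes that use these tests are in section 6.2. Item (7) is "the time from the first dose to the first observation of white blood cell count returning to normal". Item (8) is "the time from the first dose to the first observation of platelet count returning to normal". Item (4), RNA negative conversion time, is listed with no test days. Section 10 estimates time-to-event outcomes by Kaplan-Meier and compares groups by the log-rank test, two-sided at 0.05.

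**The concern.** A laboratory recovery can be dated only to a day on which blood was taken. A centre that takes the opening words of section 5.2 as an instruction can record D1, D2, D3, D4 or D5. A centre that follows section 3.2 and the flow chart can record only D5 or the discharge test. Two patients who recover at the same moment then get different event times.

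If this only added noise across centres it would matter less. But section 4.4 forms the cohorts from actual prescription, without randomisation, and section 9.2 expects about 10 hospitals from different regions and levels. If centres that prescribe more of one treatment also test more often, that treatment's laboratory recovery looks faster with no true difference, and the log-rank test cannot separate the two explanations. The two readings also differ in the number of blood draws a patient has.

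**Working it through.** The protocol gives no sample size, event rate or power figure, so there is no stated number to reproduce. The check is of the mechanism and its possible size.

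**From the protocol:** the two readings of the schedule, the first-observation rule, the log-rank test and two-sided 0.05.

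**Assumed, not in the protocol:** exponential true recovery, identical in both groups, with median m = 2, 3 or 4 days; 50, 100 or 200 patients per group; the share of each group tested daily. The sparse schedule is taken as D5 only, with censoring at D5.

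**Step 1: recorded time for the same true recovery.** Let S(t) = 0.5^(t/m).

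- Recovered by D5 = 1 − S(5).
- Under daily testing the recorded day is the true time rounded up. Its mean among those recovered by D5 is [S(0) + S(1) + S(2) + S(3) + S(4) − 5·S(5)] / [1 − S(5)].
- For m = 2: (1 + 0.707 + 0.500 + 0.354 + 0.250 − 5 × 0.177) / 0.823 = 1.926 / 0.823 = 2.34 days.
- Under D5-only testing every such recovery is recorded as day 5.
- Share recorded strictly earlier under daily testing = [1 − S(4)] / [1 − S(5)]. For m = 2: 0.750 / 0.823 = 91%.

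| Assumed median | Recovered by D5 | Mean recorded day, daily | Mean recorded day, D5 only | Recorded earlier if daily |
|---|---|---|---|---|
| 2 days | 82% | 2.3 | 5.0 | 91% |
| 3 days | 69% | 2.6 | 5.0 | 88% |
| 4 days | 58% | 2.7 | 5.0 | 86% |

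**Step 2: effect on the group comparison.** Log-rank rejection rate with no true difference, 1000 simulated trials per cell, 100 per group:

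| Share tested daily, group A / group B | m = 2 | m = 3 | m = 4 |
|---|---|---|---|
| 50% / 50% | 4.2% | 4.5% | 4.7% |
| 60% / 40% | 30.9% | 13.1% | 9.2% |
| 70% / 30% | 79.8% | 41.9% | 23.3% |
| 100% / 0% | 100% | 99.4% | 85.4% |

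At 60%/40% the rates for m = 2, 3 and 4 are 17.7%, 9.5% and 6.5% with 50 per group, and 54.5%, 24.7% and 14.2% with 200 per group. The artefact therefore grows with sample size. With an equal mix, all sizes lie between 4.2% and 6.8%. The simulation standard error at 5% is √(0.05 × 0.95 / 1000) = 0.7 percentage points, so these values are close to nominal.

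**Step 3: what one schedule does.** Equal testing density in both groups removes the artefact. If the single schedule is D5/discharge only, each patient has one post-baseline test that decides the outcome. The data then say whether recovery had happened by that test, not when it happened.

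**The case against.** The strongest reply is that there is one schedule and a loose phrase. The 5.2 sentence names the specific tests at D5 or before discharge straight after its opening words, and that clause would be largely redundant if the same tests were due daily. Section 3.2 and the flow chart agree with it, and section 5.2 also schedules stored blood only at D0 and at D5 or before discharge. This stands. A reader might infer that the protocol prescribes two schedules outright. The text does not support that: most of it points one way, and the opening words only permit the other reading. They are still current text, in the summary as well as in 5.2, and they attach laboratory work to daily follow-up.

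Second, differing density biases the cohort comparison only if it is associated with cohort. Section 4.4 does not say that cohorts cluster by centre. Sections 9.1.2, 9.3.2 and 9.4 provide for a unified SOP, monitoring and training. Section 9.1.4 provides for stratified, multivariable and propensity-score methods, and whether centre enters them may be left to the analysis plan. This stands as a limit on likelihood. It does not remove the point, because an SOP has to implement a schedule and the protocol leaves that schedule open to two readings.

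Third, a test before a discharge earlier than D5 would bring the sparse times forward, so the 5.0-day comparator is at the upper end. This stands.

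Fourth, items 4, 7 and 8 are not among the three outcomes the protocol emphasises, and only items 7 and 8 carry the first-observation wording. This also stands. RNA conversion nevertheless depends on test days, whatever its wording.

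**Conclusion.** The passages need to be reconciled, and the matter is more than clerical, because the reading a centre follows determines the recorded recovery time. The direction is certain: testing more often never records a later first normal value. The effect on the cohort comparison is conditional. It needs an association between testing density and cohort, which the design allows and the protocol does not show. Under the stated assumptions with 100 per cohort, false positives are about 9–31% at a 60%/40% split, higher at more extreme splits, and about 5% with an equal mix.

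A reader might take the 85–100% in the last row of the second table as the expected error rate. The documents do not support that. It requires every patient in one cohort to be tested daily and none in the other, and the medians, cohort sizes and shares are all assumed.

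**What to change.** State one laboratory schedule in the same terms in the program summary, section 3.2, section 5.2 and the flow chart, applying to every centre and cohort. Which schedule it should be is for the sponsor and is not judged here.

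Then define RNA negative conversion, white-cell recovery and platelet recovery on that schedule's test days:

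- If the schedule is D5/discharge only, report the proportion normal or negative at that test, accounting for the day on which it was actually done, or use interval-censored methods. Do not present a Kaplan-Meier/log-rank time. The discharge day differs between patients, so D5/discharge is not a common day in itself.
- If the schedule is daily, date the event on those common days in all cohorts.
- Keep extra routine-care samples as descriptive data in either case.

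The cost is wording in four places and one analysis rule. There are two real downsides. Extra samples do not contribute to the comparison. Under a D5/discharge-only schedule, the time-to-recovery outcomes become essentially binary, and the sponsor should accept that knowingly when settling the schedule.

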## 6 Observation items and evaluation during the study period

### 6.1 Clinical characteristics

- (1) Patient demographic characteristics: gender, age, height, weight, ethnicity, etc.;
- (2) Epidemiological data: living in chikungunya fever endemic areas or having a travel history to epidemic areas within 12 days, and having a history of mosquito bites 12 days before onset of illness;
- (3) Past medical history and treatment history: past medical history, past medication history, surgical history, allergy history, history of adverse drug reactions, etc.;
- (4) Concomitant diseases and medications: disease name, treatment drugs, purpose of medication, method of medication, time of medication, etc.
- (5) The current illness situation: onset time, highest axillary temperature within 72 hours before consultation, and diagnosis and treatment.

### 6.2 Effectiveness Observation Items

**(1) Joint swelling and pain relief rate: After the first dose, DAS 44 score was < 1.6, and decreased by more than 0.6 before and after treatment.**

Disease Activity Score of 44 Joints Based on CRP (DAS 44 -CRP): It assesses the degree of joint swelling and pain. The calculation formula is as follows:

$$\text{DAS44 - CRP} = 0.54 \times \sqrt{RAI} + 0.065 \times \sqrt{SJC44} + 0.17 \times \ln(CRP + 1) + 0.072 \times GH + 0.45$$

**44 assessed joints:** including both hand metacarpophalangeal joints (MCP1-5), proximal interphalangeal joints (PIP2-5), thumb interphalangeal joints, both wrists, both elbows, both shoulders and both knees, as shown in the figure below:

**Swollen joint count (SJC):** The number of swollen joints among 44 joints was recorded .

**CRP level:** Record laboratory test results in mg/dL (CRP).

**VAS score:** Patients mark the disease activity on a 0-100 mm visual analog scale based on their own feelings, with 0 representing no activity and 100 representing extreme activity.

2) Disease activity grading of joint swelling and pain (based on DAS 44 score):

Low activity ( DAS 44 < 1.6 )

Moderate activity ( 1.6≤DAS44 < 2.4 )

High activity ( 2.4≤DAS 44 ≤ 3.7 )

Severe activity (DAS 44 > 3.7 )

3) Evaluation of treatment response at the time of disease remission (based on reduction in DAS 4 score):

Good response (DAS 44 >1.2)

General response (0.6<DAS 44 ≤1.2)

No response (DAS 44 ≤ 0.6)

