	D5 or before discharge: complete blood count, CRP, and chikungunya nucleic acid tests; Follow-up after treatment; telephone follow-up on D7, D14, and D28.
General information and medical history	1. Demographic information: gender, age, height, weight, ethnicity, etc.; 2. Medical history: past medical history, current medical history, epidemiological history and allergy history.
Effectiveness evaluation	

1. Joint Pain and Swelling Relief Rate (DAS44 Score)

2. Change in Rash Severity (Modified EASI Score)

3. Time to Complete Fever Resolution

4. Time to Viral RNA Clearance (RT-PCR Negative)

5. Recovery of Laboratory Markers

6. Time to Symptom Recovery

7. Incidence of Complications

Safety evaluation	Incidence of adverse events/adverse reactions.

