#### 3.1 Sample size

Routine observation: all patients that can be collected during the observation period.

Maximum observation period: 28 days.

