## 10 Statistical analysis

SAS version 9.4 or above was used for data statistical analysis.

All statistical tests were two-sided, and  $P < 0.05$  was considered to be statistically significant.

The description of quantitative indicators will calculate the number of cases (N), mean (Mean), standard deviation (SD), median (Median), minimum (Min) and maximum (Max). When comparing between groups, t-test or analysis of variance was used. The description of categorical indicators uses the number of cases (N) and percentage (%) of each category. When comparing between groups, chi-square test or Fisher's exact probability method was used. The Kaplan-Meier (KM) test was used to estimate the survival function and calculate the median time for time-to-event variables. The survival curves between different groups were compared based on the Log-Rank test, and the corresponding P value was calculated.

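### The joint outcome is compared between cohorts only as a relief rate and grades; a baseline-adjusted comparison of the DAS44-CRP score should stand beside it

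*Protocol*

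**What the plan says.** The first effectiveness item in Protocol section 6.2, also first in the Program Summary list, is a rate: "Joint swelling and pain relief rate: After the first dose, DAS 44 score was < 1.6, and decreased by more than 0.6" between the assessments before and after treatment. The underlying measure is a numerical score: "Disease Activity Score of 44 Joints Based on CRP (DAS 44 -CRP): It assesses the degree of joint swelling and pain".

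The same section also grades each patient, with four levels of disease activity (cuts at 1.6, 2.4 and 3.7) and three levels of response by size of fall (cuts at 0.6 and 1.2). Neither the mean score nor its mean change is listed as an outcome.

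Section 10 gives general rules by type of variable. For quantitative indicators: "When comparing between groups, t-test or analysis of variance was used". For categorical ones: "When comparing between groups, chi-square test or Fisher's exact probability method was used". Tests are two-sided at 0.05. Section 9.1.4 separately foresees stratification, standardisation, multivariable and propensity-score methods against confounding.

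Section 3.1 sets no number: "Routine observation: all patients that can be collected during the observation period". Section 4.4 mentions a target per group but gives no value. No outcome is named primary.

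**The concern.** The relief rate applies two cuts at once and discards distance from either. A patient who goes from 3.6 to 1.7 falls by 1.9, a good response on the protocol's own grading, but is not relieved because 1.7 is above 1.6. A patient who goes from 2.2 to 1.59 falls by 0.61, only the middle response grade, but is relieved. The printed formula cannot go below 0.45, so a patient who starts at 1.05 or lower can never be relieved.

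With no sample size or power target, precision on this outcome depends on how many patients arrive and on how the data are analysed. If cohorts are moderate and treatment moves the whole distribution a little, a real difference in joint activity could be missed on the rate although the score would show it. The cohorts are not randomised, so their D0 scores may differ. Neither a crude comparison of rates nor a t-test adjusts for that.

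**Working it through.** The protocol has no sample size or power to reproduce. Everything below therefore rests on assumptions, apart from the cuts (1.6 and 0.6), the constant 0.45, the coefficient 0.072 and the two-sided 5% level.

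**Assumptions.** DAS44-CRP SD 0.9 at D0 and D5; D0-D5 correlation r of 0.3 or 0.6; true difference 0.3 at D5, as a uniform shift; floor 0.45; five pairs of D0/D5 means; equal cohorts.

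**Cohort size for 80% power with the D0-adjusted score.** Residual SD = 0.9 × √(1 − r²), and n = 2 × (1.96 + 0.8416)² × SD² / 0.3².
- r = 0.3: SD 0.859, n = 2 × 7.849 × 0.737 / 0.09 = 128.6, so 129 per cohort.
- r = 0.6: SD 0.72, n = 2 × 7.849 × 0.5184 / 0.09 = 90.4, so 91 per cohort.

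**Simulated power, two cohorts (3000 runs each), relief rate by chi-square against ANCOVA on D5 adjusted for D0.**

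| D0/D5 mean | r = 0.3: rate, ANCOVA (loss) | r = 0.6: rate, ANCOVA (loss) |
|---|---|---|
| 2.8/2.4 | 0.46, 0.79 (33) | 0.39, 0.79 (40) |
| 2.8/1.8 | 0.57, 0.80 (23) | 0.48, 0.78 (30) |
| 3.5/2.4 | 0.48, 0.79 (31) | 0.38, 0.78 (40) |
| 2.4/1.4 | 0.51, 0.76 (25) | 0.46, 0.76 (30) |
| 3.5/3.0 | 0.29, 0.81 (52) | 0.25, 0.80 (55) |

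The loss is 23 to 55 points. With three cohorts shifted by 0, 0.15 and 0.3, power is 36-53% for the rate and 78-81% for the adjusted score.

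**How much is the cut, and how much is missing baseline adjustment.** An unadjusted t-test on change has SD 0.9 × √(2(1 − r)).
- r = 0.6: SD 0.805, standard error 0.805 × √(2/91) = 0.119, power about 0.71.
- r = 0.3: SD 1.065, standard error 1.065 × √(2/129) = 0.133, power about 0.62.

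Simulated with the floor, these powers run from 0.51 to 0.71. At r = 0.3 the rate then loses nothing against the change score for means 2.8/1.8 (0.57 each) or 2.4/1.4 (0.54 against 0.51). Elsewhere it loses 10-47 points. So in some scenarios all of the loss is the missing adjustment, and in others most of it is the cut.

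**Larger cohorts.** At 400 per cohort the adjusted score has about 100% power. The rate has 0.91-0.99 in four of the five pairs of means (loss about 1-9 points). In the fifth, 3.5/3.0, it has 0.69-0.78.

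**A different effect.** If treatment instead brings an extra 20% of patients into remission, at the same n the rate has 0.70-0.99 power against 0.63-0.90 for ANCOVA in three of the pairs. The two are about equal for 2.8/1.8.

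**The printed score.** The joints named in section 6.2 are MCP 10, PIP 8, thumb interphalangeal 2, wrists 2, elbows 2, shoulders 2 and knees 2. That makes 28, not 44. If GH is the 0-100 mm scale described there, 0.072 × 100 = 7.2, so GH alone can take the score to 7.2 + 0.45 = 7.65. A score below 1.6 then needs GH below (1.6 − 0.45) / 0.072 = 15.97 mm even with no affected joint and CRP of zero. An assumed GH SD of 20 mm would by itself contribute 1.44, so the SD of 0.9 used above does not fit the formula as printed.

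**The case against.** The strongest reply is that a responder rate built on the protocol's own low-activity and response cuts is a legitimate clinical choice, easy to read, and not an error for want of a cited guideline. That stands, and it is why the rate should be kept.

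A reader might infer that the protocol keeps nothing but relieved or not relieved. It does not say so: the activity and response grades separate the patients in the examples above. They are still categories, so they recover only part of the information.

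A reader might also infer that chi-square is the only comparison planned. Section 10 is a general rule, section 9.1.4 foresees adjusted methods, and detailed modelling may sit in a statistical analysis plan that is not at hand. Adjusting a binary outcome, however, does not restore what the cut removed, and section 6.2 is where the outcome itself is fixed.

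Finally, enrolment is open-ended in an outbreak with 1,873 confirmed cases in one city by 19 July. Large cohorts would make the loss small in most scenarios. That is possible, but nothing in the protocol secures it.

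**Conclusion.** The point holds in a conditional form. The listed joint outcomes are all categories cut from a numerical score, and no comparison of the score between cohorts is listed. Under a fairly uniform shift, with cohorts sized to give the adjusted score about 80% power, the rate gives up about 23 to 55 points.

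It would be tempting to say that this study loses that much power, or that a real effect is likely to be missed. The documents do not support either: they give no sample size, SD, effect or expected rate, and other assumptions equally compatible with them give anything from a large loss to a reversal. Nor does first place in the list make the relief rate a primary outcome. What remains is a specific, inexpensive improvement to the plan.

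**What to change.** First reconcile the printed score in section 6.2: the 44 joints against the 28 listed, and the GH scale against its 0.072 coefficient. Also confirm that the joint and GH components are recorded at D0 and at D5/discharge. The flow chart has no row that names them, although the relief rate already needs the score before and after treatment.

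Then, in 6.2(1) and section 10, add a between-cohort comparison of the D5/discharge DAS44-CRP, adjusted for the D0 score and for the confounders to be handled under section 9.1.4. Report it as an adjusted mean difference with its 95% CI. Keep the relief rate beside it as the responder measure.

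Once the score is reconciled and its components are confirmed as collected, the cost is wording and one further analysis, with no new visit. The downside is that a mean difference is less immediately readable than a relief rate, which is a further reason to report both.

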## Program text

### 1 Background

Chikungunya fever is an acute infectious disease caused by chikungunya virus (CHIKV), transmitted by Aedes mosquitoes, and characterized by fever, rash, and joint pain. The first outbreak of chikungunya fever was confirmed in Tanzania in 1952, and the virus was isolated in 1956. The disease is mainly prevalent in Africa and Southeast Asia. Since 2004, outbreaks of chikungunya virus have become more frequent and widespread, partly because the virus has adapted to make it easier to spread through Aedes albopictus, and people of all ages are susceptible. In areas where Aedes mosquitoes exist, when Aedes mosquitoes reach a certain density and natural conditions are suitable, if CHIKV is introduced, it may cause an epidemic or outbreak.

On July 8, 2025, an imported case of Chikungunya fever occurred in Foshan, Guangdong. Till July 19th, there have been a total of 1,873 confirmed cases had been reported in Foshan. The rapid spread of the epidemic has brought certain treatment pressures to medical institutions. At present, there are no available vaccines or specific drugs in China, and the clinical treatment plan is mainly symptomatic treatment. In order to effectively respond to the recent surge in Chikungunya fever patients in medical institutions, the Chinese medicine expert team of Guangdong has discussed and formed a Chinese medicine agreement formula plan and applied it in clinical practice. In order to evaluate the effectiveness of this plan, this observational study is planned to be carried out.

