###### 4.1.1 Basis of diagnosis

- 1) Epidemiological data: living in Chikungunya fever endemic areas or having a travel history to epidemic areas within 12 days, and having a history of mosquito bites within 12 days before onset of the disease.
- 2) Clinical manifestations: Acute onset, with fever as the first symptom, rash appears 2 to 5 days after the disease, and severe pain in multiple joints.
- 3) Lab assessment: Chikungunya RNA detection from patient blood samples.

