###### 4.1.2 Diagnostic criteria

- 1) Suspected diagnosis: patients with the above-mentioned epidemiological history and clinical manifestations; or patients without epidemiological history but with the above-mentioned typical clinical manifestations.
- 2) Confirm the diagnosis: Patients with positive result of Chikungunya virus nucleic acid.

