##### 4.2 Inclusion Criteria

- (1) Meets the suspected or confirmed diagnostic criteria for chikungunya fever;
- (2) Symptom onset  $\leq$  3 days before enrollment;
- (3) Actual prescribed treatment aligns with the study's group assignment (Chinese medicine, Western medicine, or combined therapy);
- (4) Sign the informed consent form.

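### The DAS44 joint relief rule sets no joint-involvement condition at D0, so some patients can never meet it and some with no affected joint can

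*Protocol*

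**What the plan says.** Section 6.2(1) of the protocol defines the first-listed, bolded effectiveness item, the joint swelling and pain relief rate. After the first dose the "DAS 44 score was < 1.6, and decreased by more than 0.6 before and after treatment". Of the score itself the section says: "It assesses the degree of joint swelling and pain". The printed formula has two joint terms (RAI and SJC44), a CRP term, a GH term and a constant. GH is not defined; the only candidate input is the VAS paragraph, in which "Patients mark the disease activity on a 0-100 mm visual analog scale based on their own feelings".

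Entry does not depend on joint status for every patient. Section 4.2 asks that the patient "Meets the suspected or confirmed diagnostic criteria for chikungunya fever". The suspected route needs the clinical picture in section 4.1.1, which includes "severe pain in multiple joints". The confirmed route in section 4.1.2 needs only the RNA result: "Confirm the diagnosis: Patients with positive result of Chikungunya virus nucleic acid". Section 4.4 takes all eligible patients into the cohorts, which follow actual prescription.

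**The concern.** A relief rate for joint swelling and pain should describe patients who have something in the joints to relieve. With no such condition, the rule as printed can misclassify in two ways:

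- **Never-responders.** A low D0 score leaves no room for a fall of more than 0.6, so the patient counts as a failure whatever happens.
- **Relief without joint disease.** A patient with no affected joint can meet the rule because general health or CRP improved.

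Treatment is not randomised. If the share of such patients differs between the three cohorts, the crude rates differ for a reason other than treatment. The confounding methods named in section 9.1.4 help only if baseline joint status is among the adjustment variables. Section 4.7(4) leaves further exclusion criteria to data review, and section 8.6 discusses the data sets there. A joint condition not fixed beforehand could therefore be chosen once outcomes and treatment are known.

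**Working it through.** The protocol gives no expected rate or sample size for this endpoint, so there is no stated figure to reproduce. The check applies the printed formula and rule directly.

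**Inputs (section 6.2).** DAS = 0.54×√RAI + 0.065×√SJC44 + 0.17×ln(CRP+1) + 0.072×GH + 0.45, with CRP in mg/dL. Relief: DAS < 1.6 and fall > 0.6. Assumptions: RAI is the tenderness term; GH is the VAS, taken first as printed (0-100 mm) and then as 0-10.

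**1. Floor.** With every term at zero, DAS = 0.45. From a D0 score of 1.05 the largest possible fall is 1.05 − 0.45 = 0.60, which is not more than 0.6. So D0 ≤ 1.05 can never meet the rule, on any GH scale.

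**2. Some joint disease lies below that limit** (all other terms zero).
- RAI 1: 0.54 + 0.45 = 0.99, maximum fall 0.54.
- SJC44 = 44: 0.065×√44 + 0.45 = 0.88, maximum fall 0.43.

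**3. When a joint-free patient starts at or below 1.05.** GH ≤ (0.6 − 0.17×ln(CRP+1))/0.072, which is 8.3, 6.7, 5.7 and 4.1 at CRP 0, 1, 2 and 5. On 0-100 mm that is a narrow strip at the bottom of the scale. On 0-10 it covers much of the scale.

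**4. Relief with RAI 0 and SJC44 0.** The GH fall must exceed (0.6 − 0.17×ln((CRP at D0 + 1)/(CRP after + 1)))/0.072. That is 8.3 at unchanged CRP, 6.7 if CRP goes from 2 to 0.5, and 5.1 if it goes from 5 to 0.5. The final GH must also be below (1.15 − 0.17×ln(CRP+1))/0.072, which is 14.3 at CRP 1.

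| GH scale | GH | CRP | DAS | Fall | Relieved? |
|---|---|---|---|---|---|
| 0-100 mm | 20 to 10 | 1, unchanged | 2.008 to 1.288 | 0.720 | yes |
| 0-10 | 9 to 0 | 0, unchanged | 1.098 to 0.450 | 0.648 | yes |
| 0-10 | 8 to 1 | 5 to 0.5 | 1.331 to 0.591 | 0.740 | yes |
| 0-10 | 7 to 1 | 2 to 0.5 | 1.141 to 0.591 | 0.550 | no |

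**5. The GH scale itself.** With no affected joint and CRP 0, GH 46 mm gives 0.072×46 + 0.45 = 3.76. That is above the 3.7 limit for the protocol's top activity grade.

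**6. Unchanged joints.** RAI 1, SJC44 1, CRP 0, GH 15 to 5 mm: 0.54 + 0.065 + 1.08 + 0.45 = 2.135, then 0.54 + 0.065 + 0.36 + 0.45 = 1.415. The fall is 0.72, so the patient is relieved although neither joint term moved.

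**7. Possible size (illustration only; all shares and rates are assumed).** With 70% relief in all other patients, the crude difference between two cohorts shifts by (difference in affected share) × (relief rate among the affected − 70%). For shares of 2% and 4% this is 0.02 × (0 − 0.70) = −1.4 points if none of the affected respond, and 0.02 × (0.90 − 0.70) = +0.4 if 90% do. For 5% and 10% it is −3.5 and +1.0.

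**The case against.** **The denominator may be set elsewhere.** Section 6.2(1) gives a responder rule and does not say that every enrolled patient is in the rate. A statistical analysis plan, not shown, could restrict the set. This stands as a caution: if it already does so, part of the fix is done. It does not remove the point, because the rule is stated in full and misclassifies when followed.

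**The two harms trade off.** A reader might infer that both operate at full strength together. The arithmetic does not support that. On 0-100 mm, joint-free relief is easy and never-responders are few. On 0-10, never-responders are more common, and joint-free relief needs a very large GH fall or a combined GH and CRP fall.

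**Easy false relief comes mainly from the VAS scale.** This stands, and it is why reconciling the scale comes first. Reconciliation alone does not finish the matter, since the floor at 1.05 remains on either scale.

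**The fall of more than 0.6 is already an implicit baseline condition.** Partly true: it stops patients counting as relieved merely because they started low. But unless the denominator excludes them, those starting at 1.05 or below stay in it as certain failures.

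**Those below 1.05 have no joint disease, so they could simply be excluded.** A reader might infer this, but step 2 shows otherwise. A 1.05 cut in the main rate would drop genuine joint involvement.

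**Conclusion.** The point holds in limited form. Section 6.2(1) sets no joint-involvement condition at D0, although the confirmed route admits patients without joint signs. Any D0 score of 1.05 or less cannot meet the rule, and a patient with no affected joint can. Both statements are exact consequences of the printed formula; how often each occurs depends on the unresolved GH scale.

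The share affected cannot be derived. Section 1 describes the disease as "characterized by fever, rash, and joint pain", and the suspected route requires joint pain, so joint-free patients are probably a minority. It would also be too much to say that the comparison is biased towards a particular cohort: the documents give no D0 joint status by cohort and fix no direction. Severity is minor to moderate. The defect in the definition is certain, its effect is of unknown size, and the repair is cheap.

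**What to change.** 1. First reconcile the 0-100 mm VAS with the 0.072×GH term, and state in section 6.2(1) what GH is and on which scale it enters.
2. Compute the relief rate among patients with at least one tender or swollen joint at D0. Report by group the number outside this set, and give the all-enrolled rate as a sensitivity analysis.
3. Do not use 1.05 as an exclusion in the main rate. Report by group how many patients with joint involvement start at 1.05 or below and so cannot meet the rule, with a sensitivity analysis leaving them out.
4. Report the change in RAI and in SJC44 by group, because step 2 does not remove patients with unchanged joints who meet the rule through GH and CRP.

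Fix this before data review. The cost is a few sentences in section 6.2(1), using data the endpoint already needs, and a somewhat smaller denominator. The flow chart has no DAS44 row, so confirm there that RAI, SJC44 and GH are collected at D0.
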